- (i) (a) **HIV testing** and (b) SRH-related prevention services uptake among adolescent girls aged 16-19 in up to 9 intervention schools (with enhanced HIVST, PrEP, and contraceptive method offerings) compared to up to 9 control schools using a quasi-experimental difference-in-difference approach; and
- (ii) **linkage to care and treatment, and viral load suppression and retention at 6, 12, and 24 months** through a cohort model using pre-existing SmartCare data on HIV+ individuals in care to match to adolescent girls aged 16 and over from the same district (Lusaka) who are identified to be HIV+ at any time during SKILLZ Girl or SKILLZ Club participation and enrolled in SKILLZ-Plus.

This will be achieved by i) using a quasi-experimental difference-in-difference approach that compares girls aged 16 and over in 9 SKILLZ control schools compared to 9 schools where enhanced SKILLZ will be delivered with the enhanced HIVST and a variety of contraceptive method offerings; and ii) through a cohort model using pre-existing SmartCare data on HIV+ individuals in care to match to adolescent girls aged 16 and over from the same district (Lusaka) who are identified to be HIV+ at any time during SKILLZ-Girl or SKILLZ-Club participation.

Aim 2: Examine how the intervention works including lessons learned for future implementation by

- (i) conducting a process evaluation to identify mediators, predictors, and barriers to uptake of the SKILLZ-Girl, Club, and Plus curricula both quantitatively through mediation and moderation analyses and qualitatively through a sequential explanatory approach using focus groups discussions, interviews and observation with coaches and girls; and by
- (ii) monitoring fidelity

Aim 3: Estimate the short- and long-term cost-effectiveness and return on investment of the SKILLZ Girl, Club, and Plus curricula for improving health outcomes for adolescent girls.

8. Methodology

a. Study design

We will conduct a mixed-methods evaluation of the SKILLZ intervention using the following approaches:

A **quasi-experimental cohort** of school-aged 16-year old and over females to be followed for a two-year period will be evaluated with a difference-in-difference (DID) approach to estimate HIV testing uptake and sexual/reproductive health services use. Primary and secondary outcomes will be measured at several

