Difference-in-difference model. The primary outcome is the probability of testing for HIV at any time during the period when SKILLZ is delivered through to 24 months after the final soccer event. The primary analysis for Aim 1 will follow a difference-in-difference (DID) effect between study arms. The outcome of interest will be regressed on an indicator of study arm assignment interacted with a dichotomous variable POST which indicates the outcome after the intervention is implemented; this differentiates baseline and end-line for each study arm, controls for any time dependent variables that might confound the effect, as well as any time-invariant observed or unobserved confounders that might differ between study arm schools. Because of this, the DID is robust to time-invariant unobservable confounders (e.g., school quality) and time trends (e.g., secular increase in testing). Our estimator relies on the assumption of common time trends across intervention and control in absence of the intervention, and of static population. Additionally, we control for baseline individual and school-level moderators that may be unbalanced at baseline after randomization. School-level controls include size, promotion rates, sex composition and repetition and dropout rates (available in the district education office) and individual girls' controls include age, grade, maternal education, HIV knowledge. Clustering by school will be accounted for by a generalized estimating equation approach. We will estimate intention-to-treat (ITT) by including all girls in the evaluation cohort assigned to each arm rather than all girls who actually participated in SKILLZ.

Individual-level matched cohort analysis for HIV-infected: The analysis will follow an individual ITT estimator among individuals found to be HIV-infected, who will then be matched (based on clinic, age, ART state date, and gender) to HIV-infected individuals in the SmartCare database. The outcomes are the proportion of enrolled HIV+ girls who linked to care, who are virally suppressed and retained in care at 6, 12, and 24 months after diagnosis of HIV+ (using national electronic HIV medical record data). We will conduct an ITT analysis for the logistic probability of being suppressed at 6, 12, and 24 months after HIV+ diagnosis, where girl is the unit of analysis. All data will be analyzed using STATA.

Process evaluation: This will involve quantitative and qualitative analyses:

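### Aim 1(ii) compares linkage to care with SmartCare patients who have all linked already, so that contrast cannot show a benefit; the stated ITT does not survive matching on ART start date, and no calculation supports power for this aim

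*Combined protocol and SAP*

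**What the plan says.** Section 7, Aim 1(ii), sets out to assess "linkage to care and treatment, and viral load suppression and retention at 6, 12, and 24 months", and to do so "through a cohort model using pre-existing SmartCare data on HIV+ individuals in care to match to adolescent girls". Section 8c (the paragraph on girls found to be HIV-infected) repeats that the impact of SKILLZ-Plus on linkage, retention and viral load will be measured and compared with an existing matched cohort.

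Section 8f describes an "individual ITT estimator among individuals found to be HIV-infected", who are then "matched (based on clinic, age, ART state date, and gender) to HIV-infected individuals in the SmartCare database". Section 4 gives the same matching list with ART start date, so the word in 8f is a typing error.

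Two items are stated in two ways:

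- **Cohort.** The Aim 1(ii) bullet takes girls "who are identified to be HIV+ at any time during SKILLZ Girl or SKILLZ Club participation and enrolled in SKILLZ-Plus". The paragraph that follows restates the aim without the enrolment condition. Section 8f uses both the ITT wording above and "The outcomes are the proportion of enrolled HIV+ girls who linked to care".
- **Start of follow-up.** Section 8f counts girls as "retained in care at 6, 12, and 24 months after diagnosis of HIV". Section 8c allows either diagnosis or the date on which the programme identifies the girl as positive.

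Section 8c (Study Population) also says that the sample is powered for the primary endpoints in Aim 1ii and points to calculations further on.

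**The concern.** A comparator must have an ART start date to be matched, and must be in care to be eligible. Both conditions require that linkage has already happened, so an outcome of the comparison is fixed in one group by the way that group is selected.

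The same condition acts on the girls. A girl who tests positive and never starts ART has no value on a matching variable, yet an ITT set has to contain her. She matters to the question, because Section 4 presents better linkage as the first feature of SKILLZ-Plus.

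At stake is whether Aim 1(ii) can say anything comparative about linkage, and whether its suppression and retention results describe all girls found positive, those who enrolled, or those who started ART.

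**Working it through.** **1. Ever-linked contrast.** Comparators: 100% by selection. Let L be the share of HIV-positive girls who link, and suppose SKILLZ-Plus has no effect.

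- Girls with no ART date drop out at matching: the girls left are also 100% linked, and the difference is 0 whatever the truth.
- They are kept unmatched: the difference is L − 100. The only linkage rate in the documents is 95% (Section 3c, male and female youth, 2010–2012), which gives −5 points. At an assumed 80% it is −20.

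Neither route can give a positive difference. Linkage has no time-bound definition. A timed version would not fix comparators at 100%, but they would still be selected as eventual linkers, and it would need their diagnosis dates. Section 8e names ART initiation date among the SmartCare fields but not diagnosis date; that list is introduced as examples and may be incomplete.

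**2. ITT for suppression and retention.** Dropping girls who never start ART is not ITT. Keeping them as failures against comparators who all started ART gives, with no true effect, a deficit of comparator rate × (1 − L). At L = 95%:

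- Suppression at 34% (Section 1a, not limited to people on ART): 0.34 × 0.05 = 1.7 points.
- 24-month retention at about 50% (Section 5): 0.50 × 0.05 = 2.5 points.

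Lower assumed linkage scales this up; at 80% the figures are 6.8 and 10 points.

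**3. Start of follow-up.** The date of identification by the programme has no counterpart in SmartCare. Section 4 admits girls with a previously known diagnosis, who may already be on ART. If their months run from identification while a comparator's run from diagnosis or ART start, they have had longer on treatment at each time point. That pushes towards SKILLZ-Plus, against the direction in step 2.

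**4. What is calculated.** Two calculations appear in Section 8c, and both belong to Aim 1(i).

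- HIV testing, 60% against 80%, ICC 0.1, 9 schools of 100 per arm: design effect 1 + 99 × 0.1 = 10.9; effective n = 900/10.9 = 82.6; power 80.7% (two-sided 0.05). Reproduced.
- Contraceptive use: (351/0.25) × 2 = 2,808; × 1.125 = 3,159. Reproduced with the 12.5% attrition in the text (the printed factor of 1.025 gives 2,878).

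Nothing is calculated for HIV-positive girls.

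**5. What Aim 1(ii) could detect.** About 2% of testers are expected to be positive (Section 8a). Average testing is (60 + 80)/2 = 70% with equal arms.

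| Girls | HIV-positive = N × 0.70 × 0.02 |
|---|---|
| 1,600 (16 schools × 100) | 22.4 |
| 1,800 (18 schools × 100) | 25.2 |
| 3,200 (survey target, Section 8d) | 44.8 |

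The detectable rise is the smallest d = p1 − p0 for which Φ{[d − 1.96 √(2p̄(1 − p̄)/n)] / √[(p1(1 − p1) + p0(1 − p0))/n]} ≥ 0.80, with p0 = 0.34, p̄ the mean of p0 and p1, 1:1 matching assumed, and pairing and losses ignored. Example, n = 22, d = 0.41: (0.41 − 1.96 × 0.1501)/0.1368 = 0.846, power 80%.

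| n | Rise, 1:1 | Rise, 1:4 |
|---|---|---|
| 22 | 41.0 points | 32.5 points |
| 25 | 38.7 points | 30.5 points |
| 45 | 29.2 points | 22.8 points |

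**The case against.** **The linkage bias can be overstated.** A reader might infer that SKILLZ-Plus is bound to show a large linkage deficit, of 20 or 30 points. The documents do not support that. Read literally, Section 8f sends the girls through the match, those with no ART date fall out, and the result is a tie. A deficit arises only if they are kept, and any figure above about 5 points needs a linkage rate that the documents do not give.

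**The direction for suppression and retention is not one-sided.** It is also tempting to conclude that the whole aim is biased against the intervention. Previously diagnosed girls followed from identification, or a cohort restricted to those who enrolled, could favour SKILLZ-Plus. This objection stands.

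**Section 8f can be read as one clock.** Its model counts months from HIV diagnosis and may be meant for both groups. That is fair; the gap lies in the alternative allowed by Section 8c and in the absence of any stated comparator date.

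**The power sentence may be a slip.** The next sentence concerns HIV testing, so 1ii may stand for 1i. In that case no power was ever claimed for this aim, and a one-character correction settles it. As printed, the sentence is unsupported.

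**Linkage matters too much to drop.** It is central to SKILLZ-Plus, and a different comparator could in principle preserve the contrast. That would need records of people diagnosed whether or not they linked, and the documents name no such source. Research question c in Section 6 does not ask for a linkage effect.

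**Conclusion.** The concern holds. As designed, the ever-linked comparison cannot show a benefit of SKILLZ-Plus: it is uninformative if girls without an ART date are dropped, and biased against SKILLZ-Plus if they are kept (about 5 points at 95% linkage). An ITT analysis of all girls found HIV-infected cannot be carried through a match on ART start date, and the plan does not say what happens to girls who lack one. Cohort and start of follow-up need reconciling, and until they are, the net direction of bias for suppression and retention is unknown.

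The aim is also small: about 22–25 HIV-positive girls from 1,600–1,800, or about 45 from 3,200, enough for 80% power only against rises of about 39–41 or 29 points from 34% suppression. This rests on 2% positivity among testers, 70% average testing, 1:1 matching (no ratio is stated) and the background suppression rate. Clinic-referred girls and known-positive girls who do not retest are not counted, so these are not upper limits.

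The primary HIV-testing outcome is unaffected.

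**What to change.** 1. **Linkage.** Remove it from the matched comparison in Sections 7 and 8c. Report it as a single-group proportion with a confidence interval among all girls found HIV-infected. Section 8f (fidelity monitoring) already plans to collect successfully linked referrals.
2. **Suppression and retention.** Use ART start as time zero in both groups, select comparators on having started ART and not on still being in care, and state the matching ratio. Label the result an effect among ART starters, not ITT. Report all HIV-positive girls descriptively, and count unlinked girls as failures in a sensitivity analysis.
3. **Cohort.** Use one definition in Sections 7 and 8f. If SKILLZ-Plus enrolment is required, do not count time before enrolment as exposed follow-up. State also how girls whose ART start precedes their identification enter the analysis, since their earlier time on ART is likewise unexposed.
4. **Power.** Correct or delete the Aim 1ii sentence in Section 8c and label Aim 1(ii) exploratory.

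The work is mostly wording, plus an index date that SmartCare already holds (Section 8e). The price is a narrower estimand that conditions on a step SKILLZ-Plus is meant to improve, fewer girls in the matched comparison, and no comparative claim about linkage.

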Within SKILLZ-Girl and SKILLZ-Club, our study will examine the additional benefits of offering access to two new health service offerings that are expressly designed to overcome barriers to uptake especially difficult for adolescents to overcome—HIV self-testing (HIVST) kits and access to an expanded method mix for contraceptive methods. Referral for contraceptive and SRH services will be made to the PEPFAR-funded DREAMS Houses or youth corners at local government facilities which are located within close distance to all schools where the SKILLZ package will be implemented.

Our mixed-methods evaluation will assess the effects of the enhanced SKILLZ offering (SKILLZ-Girl Enhanced & SKILLZ Club programs) compared to the SOC SKILLZ offering of SKILLZ-Girl only. Although the SKILLZ Program (Enhanced or SOC pending school allocation) will be offered to all girls enrolled in Grade 10 at selected study secondary schools, only girls aged 16 and over at the commencement of SKILLZ-Girl will be enrolled into the research study.

We will examine outcomes for school girls aged 16 and over enrolled in Grade 10 at the start of the intervention in up to 16 schools where the SOC SKILLZ Package is offered, compared to outcomes in up to 16 schools where the enhanced SKILLZ-Package is offered, including HIVST, the availability of expanded contraceptive services and the SKILLZ-Club following completion of SKILLZ-Girl. Therefore, all schools will be preassigned prior to the intervention into the following 2 categories (see **Figure 3** in *Section 8 - Methodology* below).

1. **SOC:** SKILLZ-Girl → Club SOC
2. **ENHANCED:** SKILLZ-Girl enhanced → SKILLZ-Club

Our central hypothesis is that the additional offering of HIVST and contraceptive services in an enhanced SKILLZ-Girl combined with the SKILLZ-Club offering will increase HIV testing and contraceptive uptake and continuation.

In addition to SKILLZ-Girl and SKILLZ-Club, girls testing HIV-positive at any time during the study intervention period will be additionally offered to participate in the SKILLZ-Plus facility-based curriculum for HIV-infected adolescents. The effect of the SKILLZ-Plus curriculum will be tested using a SmartCare-derived matched (i.e., on clinic, age, ART start date and gender) population.

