timepoints longitudinally across up to 9 schools offering the enhanced SKILLZ-Girl and SKILLZ-Clubs program and up to 9 schools offering the “standard of care” (SOC) SKILLZ-Girl and SOC Clubs (see Figure 3). Recruitment will take 12 months on a rolling basis. The order in which schools will be selected will be random. Participants will be clustered at the school-level; we will enroll all girls aged 16-years at the commencement of SKILLZ-Girl and in Grade 10 from each participating school.

[figure not shown]
All enrolled girls will be followed over the two-year time period to assess SRH service uptake, including HIV testing. It is estimated that the majority (~98%) of girls testing for HIV will likely be HIV-negative, based on estimates from programmatic GRS data. While HIV-positive girls will continue to participate in the school-based SKILLZ-Girl and Clubs activities and followed for SRH use, they will also be offered contemporaneous enrollment into SKILLZ-Plus upon infection; retention in care and Viral Load Suppression (VLS) at 6, 12, and 24 months will be measured for this subset. See **Figure 2** for details of enrolment flow.

Process evaluation: We will conduct a process evaluation to better understand the casual pathways and effect mediators and moderators using mixed methods approaches, including supplemental qualitative data collection. To investigate reasons why the program components (SKILLZ-Girl, Club & Plus) might fail or succeed in different schools or communities and assess intervention effect mediators and moderators for HIV testing and contraceptive use uptake we will use a mixed methods approach involving: (1) quantitative analyses of baseline survey data for testing how variables can moderate the observed impact of the intervention, and (2) qualitative data collected from a subset of SKILLZ participants in the evaluation cohort and their coaches to further understand potential mediating pathways outlined in Figure 1.

Fidelity monitoring: We will also include measures to monitor fidelity of the intervention implementation, including receptivity to and understanding of the intervention amongst participants, the perceived appropriateness and relevancy of the intervention for adolescent girls in school, and the extent to which the intervention was delivered per protocol in different communities and schools.

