Quantitative analysis: Surveys conducted at baseline will be used to identify differential effects among girls who do and do not take up services according to baseline moderating variables as specified in **Figure 1** and as assessed by previous sexual behavior, HIV testing/status, knowledge, maternal education by interacting the main exposure by these indicators. Statistical mediation will be assessed using the causal inference-based approach of Valeri et al., which yields optimal estimates of indirect effects in the presence of binary outcomes and moderator-mediator interactions,⁶⁴ and robust standard errors to address clustering of individuals within facilities, and account for multiple causally depending mediators.⁶⁵ Significant indirect and total effects of integration markers on outcomes accompanied by non-significant direct effects will signify mediation. The interplay between exposure, effect modifiers, moderators and outcomes in the causal chain is represented in **Figure 1**. For analyses, we will use mixed effect structural equation models in STATA and MPLUS with bootstrapped standard errors to test the contribution of indirect effects.

Qualitative analysis: All interviews will be voice-recorded, transcribed and coded using a thematic analysis process⁶⁶ (e.g. in NVIVO or Atlas.ti). Analysis will begin with familiarization of the data that will involve

reading and re-reading of the transcripts to understand the data. Notes will be taken down at the point of familiarization to guide the development of the codebook. Codes will be extracted both inductively (bottom-up) and deductively (top-down). Inductively, open coding will be conducted to identify interesting and meaningful text in each line of the transcripts. Each piece of text will be grouped under a specific code that describes the meaning of the text. Once all the text has been coded, the researchers will then identify themes that tell something significant about the research questions and group a set of codes under each related theme. The themes will then be reviewed by reading each code and its associated text and re-arranged or removed in order to refine the themes and their meaning. Secondary coding will be applied to uncover the latent meaning of each of the themes. Themes will then be re-coded to uncover the latent meaning of the themes and refine their definitions.

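### The mediation analysis clusters girls by facility and states its rule for an undefined exposure, although arms are allocated by school; its tests of arm effects can be too liberal, by an amount the plan leaves open

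*Combined protocol and SAP*

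**What the plan says.** Section 8f, Process evaluation, Quantitative analysis, is the only account of the mediation analysis.

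- **Standard errors:** "robust standard errors to address clustering of individuals within facilities". No other clustering unit is named there.
- **Decision rule:** "Significant indirect and total effects of integration markers on outcomes accompanied by non-significant direct effects will signify mediation". The markers are not defined, the term appears nowhere else, and no instrument in Section 8d is said to measure them.
- **Moderation, same paragraph:** effects are examined "by interacting the main exposure by these indicators", so the exposure has a different name a few lines earlier.
- **Second method, same paragraph:** "mixed effect structural equation models in STATA and MPLUS with bootstrapped standard errors to test the contribution of indirect effects". Neither the random-effect level nor the resampling unit is stated.

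Elsewhere the unit is the school. Section 4 says "all schools will be preassigned prior to the intervention into the following 2 categories", Section 8c randomizes schools, Section 8a says "Participants will be clustered at the school-level", and the difference-in-difference paragraph of Section 8f says "Clustering by school will be accounted for by a generalized estimating equation approach".

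**The concern.** Study arm varies only between schools, so the precision of an arm-to-mediator or total effect is set by the variation between schools. A robust standard error protects against this only if its clusters contain whole schools.

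Facility does not look like loose wording for school. Section 3c speaks of referral between schools and health facilities, and Section 4 and the fidelity paragraph of Section 8f use the word for health facilities. Section 8d (Youth-Friendly services electronic data) sends girls to one type of site or another according to school location, home address or preference. Girls of one school can therefore fall into different facility clusters and be treated as independent.

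Mediation is research question (e) in Section 6 and part of Aim 2 in Section 7, and the rule that answers it rests wholly on which effects are significant. Standard errors that are too small can produce false mediators. They can also make a direct effect look significant and so hide a real mediator. Separately, a rule about an undefined exposure cannot be run as written.

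**Working it through.** **Inputs from Section 8c.** About 100 girls per school, ICC 0.1, alpha 0.05 (taken as two-sided), power 80%, HIV testing 60% versus 80%, and up to 18 schools, or 16 without the two pilot schools. The ICC is given for HIV testing; none is given for a mediator.

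**The plan's own figure.** Individual randomization needs 82 girls per arm. The design effect is 1 + 99 × 0.1 = 10.9. Then 82 × 10.9 = 893.8 girls, or 8.94 schools per arm, hence 9 per arm and 18 in all. Power with 9 per arm is 80.7%. The plan's 18 schools are reproduced, so these inputs describe its own model. The protocol states no error rate for the mediation tests.

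**Formula.** Suppose each school's 100 girls are split equally over *k* facilities that no other school uses. Facility-clustered errors then reflect a design effect of 1 + (100/*k* − 1) × ICC, while the true one is 1 + 99 × ICC. The actual error of a nominal 5% test is 2 × [1 − Φ(1.96 × √(used/true))].

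At ICC 0.1 the true design effect is 10.9:

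| Facilities per school | Design effect used | 1.96 × √(used/true) | Actual error |
|---|---|---|---|
| 1 | 10.9 | 1.96 | 0.050 |
| 2 | 1 + 49 × 0.1 = 5.9 | 1.44 | 0.149 |
| 3 | 1 + 32.3 × 0.1 = 4.23 | 1.22 | 0.222 |
| 4 | 1 + 24 × 0.1 = 3.4 | 1.09 | 0.274 |
| School ignored | 1 | 0.59 | 0.553 |

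The same formula at smaller ICCs, assumed because mediators may cluster less than testing:

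| ICC | 2 facilities | 3 facilities | 4 facilities | School ignored |
|---|---|---|---|---|
| 0.05 | 0.136 | 0.194 | 0.233 | 0.422 |
| 0.02 | 0.110 | 0.145 | 0.167 | 0.256 |

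**Simulation of the total effect.** Settings: 18 schools × 100 girls, ICC 0.1, no arm effect, cluster-robust linear model, 800 runs per case.

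| Cluster used | Normal reference | t reference, 17 df |
|---|---|---|
| School | 0.075 | 0.060 |
| 2 facilities per school | 0.18 | 0.17 |
| 4 facilities per school | 0.32 | 0.31 |
| Whole schools, two to a facility | 0.09 | 0.06 |
| Girls spread at random over 9–18 shared facilities | 0.57–0.60 | 0.53–0.54 |

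The simulation error around 0.05 is √(0.05 × 0.95/800) ≈ 0.008. School clustering with a t reference is thus close to nominal, and the normal reference is somewhat liberal because there are only 18 clusters.

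**Indirect effect** (joint test of both paths, ICC 0.1). If the mediator affects the outcome but arm does not move the mediator, the error is 0.17 with two facilities per school and 0.31 with four. If neither path exists, it is 0.02 and 0.04, below nominal.

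**The case against.** **The mapping is unknown.** Section 4 places the referral sites close to all the schools, so each school may in practice have one facility, or several whole schools may share one. The excess error would then be nil, or only what comes from having few clusters. This stands, and it rules out any single multiplier. A reader might infer from the two-to-four-facility rows that the tests run at two to five times nominal. The documents do not support that: the mappings they leave open run from about 1× to about 11× (0.553/0.05) at ICC 0.1.

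**Not every test is affected alike.** The rule needs a significant indirect effect, and that test is conservative when both paths are null. This stands. The inflated case still matters, because Section 3b puts the mediators forward as pathways to the outcomes.

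**The structural equation models may respect school.** They may, given Section 8a. The plan does not say so, and facilities are the only cluster named in that paragraph.

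**It may be a slip that would surface at coding.** Section 8d envisages service records for girls who choose to use those services, so others may have no facility to cluster on. That is plausible, and it is a further reason to correct the text.

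**Aim 2 also covers SKILLZ-Plus.** That component is facility-based, takes girls from both arms and accepts clinic referrals. A blanket change to school and study arm would not fit it. This stands and limits the fix.

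**The undefined exposure does not itself inflate error.** Correct. If the markers varied between girls within a school, the figures above would change. A reader might also infer that the dataset will hold no such variable; the documents show only that the term is undefined.

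**Conclusion.** The point holds as an internal contradiction with a conditional cost. The clustering unit named for mediation is not the unit of allocation, and the exposure in the decision rule is undefined. If a school's girls are split over facilities, as Section 8d permits, tests of arm-to-mediator and total effects are too liberal. The figures in the working assume study arm as the exposure and, in the formula, an even split over unshared facilities. They borrow the HIV-testing ICC of 0.1, and the excess shrinks at smaller ICCs.

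Severity is moderate. This is a secondary process analysis. A reader might infer that the trial's main result is at risk; it is not, because the difference-in-difference analysis already accounts for clustering by school.

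**What to change.** In Section 8f, Process evaluation, Quantitative analysis, for every analysis of the effect of study arm:

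1. Replace *within facilities* with *within schools, the unit of allocation*.
2. State that school is the random-effect level in the mixed-effect models and that the bootstrap resamples whole schools within arm.
3. Use a small-sample (t) reference suited to 16–18 clusters. In the simulation this brings the error under school clustering from about 0.075 to about 0.06.
4. Replace *integration markers* with *study arm (enhanced versus SOC)*, or define the markers and say how they are measured.
5. Specify any SKILLZ-Plus mediation analysis separately, with its own exposure and clustering unit, since it is not allocated by school.

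These are changes to the analysis text only, with no new data or schools. The cost is wider intervals for the mediation effects.
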